16.2 APPENDIX B: PERFORMANCE STATUS CRITERIA

Karnofsky Performance Scale	
Percent	Description
100	Normal, no complaints, no evidence of disease.
90	Able to carry on normal activity; minor signs or symptoms of disease.
80	Normal activity with effort; some signs or symptoms of disease.
70	Cares for self, unable to carry on normal activity or to do active work.
60	Requires occasional assistance but is able to care for most of his/her needs.
50	Requires considerable assistance and frequent medical care.
40	Disabled, requires special care and assistance.
30	Severely disabled, hospitalization indicated. Death not imminent.
20	Very sick, hospitalization indicated. Death not imminent.
10	Moribund, fatal processes progressing rapidly.
0	Dead.

16.3 APPENDIX C: INHIBITORS AND INDUCERS OF CYP3A

Inhibitors of CYP3A are defined as follows. A comprehensive list of inhibitors can be found at the following website: <http://medicine.iupui.edu/clinpharm/ddis/table.aspx>. The general categorization into strong, moderate, and weak inhibitors according to the website is displayed below. Refer to Section 4.4.1 and 14.1.7 on instructions for concomitant use of CYP3A inhibitors and inducers with study medications.

Inhibitors of CYP3A	Inducers of CYP3A

Strong inhibitors:
 
INDINAVIR NELFINAVIR RITONAVIR CLARITHROMYCIN ITRACONAZOLE KETOCONAZOLE NEFAZODONE SAQUINAVIR TELITHROMYCIN
 
Moderate inhibitors:
 
aprepitant erythromycin diltiazem flucanazole grapefruit juice Seville orange juice verapamil
	
Weak inhibitors:
 
cimetidine
 
All other inhibitors:
 
amiodarone NOT azithromycin chloramphenicol boceprevir ciprofloxacin delavirdine diethyl-dithiocarbamate fluvoxamine gestodene imatinib mibepradil mifepristone norfloxacin norfluoxetine star fruit telaprevir troleandomycin voriconazole
 
Carbamazepine Efavirenz Nevirapine Barbiturates Glucocorticoids Modafinil Oxcarbazepine Phenobarbital Phenytoin Pioglitazone Rifabutin Rifampin St. John's Wort Troglitazone

Source: <http://medicine.iupui.edu/clinpharm/ddis/table.aspx>

16.4 APPENDIX D: NIH ORGAN-SPECIFIC AND GLOBAL SCORING OF CHRONIC GVHD

	SCORE 0	SCORE 1	SCORE 2	SCORE 3
PERFORMANCE SCORE: KPS ECOG LPS	 Asymptomatic and fully active (ECOG 0; KPS or LPS 100%)	 Symptomatic, fully ambulatory, restricted only in physically strenuous activity (ECOG 1, KPS or LPS 80-90%)	 Symptomatic, ambulatory, capable of self-care, >50% of waking hours out of bed (ECOG 2, KPS or LPS 60-70%)	 Symptomatic, limited self-care, >50% of waking hours in bed (ECOG 3-4, KPS or LPS <60%)
SKIN†				
SCORE % BSA				
GVHD features to be scored by BSA:	 No BSA involved	 1-18% BSA	 19-50% BSA	 >50% BSA
Check all that apply:	 Maculopapular rash/erythema  Lichen planus-like features  Sclerotic features  Papulosquamous lesions or ichthyosis  Keratosis pilaris-like GVHD			
SKIN FEATURES				
SCORE:	 No sclerotic features	 Superficial sclerotic features “not hidebound” (able to pinch)	Check all that apply:  Deep sclerotic features  “Hidebound” (unable to pinch)  Impaired mobility  Ulceration	
Other skin GVHD features (NOT scored by BSA)	Check all that apply:  Hyperpigmentation  Hypopigmentation  Poikiloderma  Severe or generalized pruritus  Hair involvement  Nail involvement			
 Abnormality present but explained entirely by non-GVHD documented cause (specify): _____				
MOUTH Lichen planus-like features present:  Yes  No	 No symptoms	 Mild symptoms with disease signs but not limiting oral intake significantly	 Moderate symptoms with disease signs with partial limitation of oral intake	 Severe symptoms with disease signs on examination with major limitation of oral intake
 Abnormality present but explained entirely by non-GVHD documented cause (specify): _____				

Abbreviated Title: Ibrutinib for Chronic GvHD

Version Date: 4/26/2023

	SCORE 0	SCORE 1	SCORE 2	SCORE 3	
EYES	 No symptoms	 Mild dry eye symptoms not affecting ADL (requirement of lubricant eye drops ≤ 3 x per day)	 Moderate dry eye symptoms partially affecting ADL (requiring lubricant eye drops > 3 x per day or punctal plugs), WITHOUT new vision impairment due to KCS	 Severe dry eye symptoms significantly affecting ADL (special eyewear to relieve pain) OR unable to work because of ocular symptoms OR loss of vision due to KCS	
Keratoconjunctivitis sicca (KCS) confirmed by ophthalmologist:	 Yes  No  Not examined				
 Abnormality present but explained entirely by non-GVHD documented cause (specify): _____					
GI Tract	 No symptoms	 Symptoms without significant weight loss* ($<5\%$)	 Symptoms associated with mild to moderate weight loss* (5-15%) OR moderate diarrhea without significant interference with daily living	 Symptoms associated with significant weight loss* $>15\%$, requires nutritional supplement for most calorie needs OR esophageal dilation OR severe diarrhea with significant interference with daily living	
Check all that apply:	 Esophageal web/ proximal stricture or ring  Dysphagia  Anorexia  Nausea  Vomiting  Diarrhea  Weight loss $\geq 5\%$ *  Failure to thrive				
 Abnormality present but explained entirely by non-GVHD documented cause (specify): _____					
LIVER	 Normal total bilirubin and ALT or AP $< 3 \times ULN$	 Normal total bilirubin with ALT ≥ 3 to $5 \times ULN$ or AP $\geq 3 \times ULN$	 Elevated total bilirubin but ≤ 3 mg/dL or ALT > 5 ULN	 Elevated total bilirubin > 3 mg/dL	
 Abnormality present but explained entirely by non-GVHD documented cause (specify): _____					
LUNGS**	Symptom score:	 No symptoms	 Mild symptoms (shortness of breath after climbing one flight of steps)	 Moderate symptoms (shortness of breath after walking on flat ground)	 Severe symptoms (shortness of breath at rest; requiring O_2)
Lung score: % FEV1		 FEV1 $\geq 80\%$	 FEV1 60-79%	 FEV1 40-59%	 FEV1 $\leq 39\%$

Pulmonary function tests

Not performed

Abnormality present but explained entirely by non-GVHD documented cause (specify): _____

Abbreviated Title: Ibrutinib for Chronic GvHD

Version Date: 4/26/2023

	SCORE 0	SCORE 1	SCORE 2	SCORE 3
JOINTS AND FASCIA	 No symptoms	 Mild tightness of arms or legs, normal or mild decreased range of motion (ROM)	 Tightness of arms or legs OR joint contractures, erythema thought due to fasciitis, moderate decrease ROM AND mild to moderate limitation of ADL	 Contractures WITH significant decrease of ROM AND significant limitation of ADL (unable to tie shoes, button shirts, dress self etc.)
P-ROM score (see below)				
Shoulder (1-7):				
Elbow (1-7):				
Wrist/finger (1-7):				
Ankle (1-4):				

Abnormality present but explained entirely by non-GVHD documented cause (specify): _____

GENITAL TRACT (See Supplemental figure [†])	 No signs	 Mild signs [‡] and females with or without discomfort on exam	 Moderate signs [‡] and may have symptoms with discomfort on exam	 Severe signs [‡] with or without symptoms
□ Not examined				
Currently sexually active				
□ Yes				
□ No				

Abnormality present but explained entirely by non-GVHD documented cause (specify): _____

Other indicators, clinical features or complications related to chronic GVHD (check all that apply and assign a score to severity (0-3) based on functional impact where applicable none – 0,mild -1, moderate -2, severe – 3)

 Ascites (serositis) _____	 Myasthenia Gravis _____	 Eosinophilia > 500/ μ l _____
 Pericardial Effusion _____	 Peripheral Neuropathy _____	 Platelets <100,000/ μ l _____
 Pleural Effusion(s) _____	 Polymyositis _____	 Others (specify): _____
 Nephrotic syndrome _____	 Weight loss >5%* without GI symptoms _____	

Overall GVHD Severity
(Opinion of the evaluator)

No GVHD Mild Moderate Severe

Photographic Range of Motion (P-ROM)

Shoulder	
Elbow	
Wrist/finger	
Ankle	

16.5 APPENDIX E: GLOBAL SCORING OF CHRONIC GVHD

Stage	Definition
Mild	1 or 2 organs involved with no more than score 1 plus Lung score 0
Moderate	At least 1 organ (not lung) with a score of 2 or 3 or more organs involved with no more than score 1 or Lung score 1
Severe	At least 1 organ with a score of 3 or Lung score of 2 or 3

In skin: higher of the 2 scores to be used for calculating global severity

In lung: FEV1 is used instead of clinical score for calculating global severity

If the entire abnormality in an organ is noted to be unequivocally explained by a non-cGVHD documented cause, that organ is not included for calculation of the global severity

If the abnormality in an organ is attributed to multifactorial causes (GVHD plus other causes) the score organ will be used for calculation of the global severity regardless of the contributing causes (no downgrading of organ severity score).

16.6 APPENDIX F: CHRONIC GvHD ACTIVITY ASSESSMENT (CLINICIAN) FORM A

CHRONIC GVHD ACTIVITY ASSESSMENT- CLINICIAN													
Health Care Provider Global Ratings:		Where would you rate the severity of this patient's chronic GvHD symptoms on the following scale, where 0 is cGVHD symptoms that are not at all severe and 10 is the most severe cGVHD symptoms possible:											
0=none 1=mild 2=moderate 3=severe	cGVHD symptoms not at all severe	0	1	2	3	4	5	6	7	8	9	10	Most severe cGVHD symptoms possible
Mouth		Erythema	None	0	Mild erythema or moderate erythema (<25%)	1	Moderate (≥25%) or Severe erythema (>25%)	2	Severe erythema (≥25%)			3	
Lichenoid		None	0	Lichen-like changes (<25%)	1	Lichen-like changes (25-50%)	2	Lichen-like changes (>50%)			3		
Ulcers		None	0			Ulcers involving (≤20%)	3	Severe ulcerations (>20%)			6		
										Total score for all mucosal changes			
Gastrointestinal-Esophageal		0= no esophageal symptoms 1=Occasional dysphagia or odynophagia with solid food or pills during the past week 2=intermittent dysphagia or odynophagia with solid foods or pills, but not for liquids or soft foods, during the past week											
Gastrointestinal-Upper GI		3=Dysphagia or odynophagia for almost all oral intake, on almost every day of the past week											
Gastrointestinal-Lower GI		0= no symptoms 1=mild, occasional symptoms, with little reduction in oral intake during the past week 2=moderate, intermittent symptoms, with some reduction in oral intake during the past week 3=more severe or persistent symptoms throughout the day, with marked reduction in oral intake, on almost every day of the past week											
Lungs (liters and % predicted)		0= no loose or liquid stools during the past week 1= occasional loose or liquid stools, on some days during the past week 2=intermittent loose or liquid stools throughout the day, on almost every day of the past week 3=voluminous diarrhea on almost every day of the past week, requiring intervention to prevent or correct volume depletion											
Bronchiolitis Obliterans		FEV1	FVC	Single Breath DLCO (adjusted for hemoglobin)									
Liver Values		Total serum bilirubin	ULN	mg/dL	ALT	ULN	U/L	Alkaline Phosphatase			ULN	Eosinophils	
Baseline Values		Total Distance Walked in 2 or 6 Mins:			Karnofsky or Lansky	Platelet Count	K/uL	Total WBC			K/uL	U/L	
 Abnormality present but explained entirely by non-GVHD documented cause (specify site/alternate cause); _____  Abnormality present but explained entirely by non-GVHD documented cause (specify site/alternate cause); _____  Abnormality present but explained entirely by non-GVHD documented cause (specify site/alternate cause); _____													

Chronic GvHD Activity Assessment (Clinician) Form A

Abbreviated Title: Ibrutinib for Chronic GvHD

Version Date: 4/26/2023

	SCORE 0	SCORE 1	SCORE 2	SCORE 3																						
SKIN GVHD features to be scored by BSA: Check all that apply:  Maculopapular rash / erythema  Lichen planus-like features  Sclerotic features  Papulosquamous lesions or ichthyosis  Keratosis pilaris-like	 No BSA involved	 1-18% BSA	 19-50% BSA	 >50% BSA																						
 Abnormality present but explained entirely by non-GVHD documented cause (specify): _____																										
SKIN FEATURES SCORE:	 No sclerotic features		 Superficial sclerotic features "not hidebound" (able to pinch)	Check all that apply:  Deep sclerotic features  "Hidebound" (unable to pinch)  Impaired mobility  Ulceration																						
If skin features score = 3, BSA% of non-moveable sclerosis/fasciitis _____ 
How would you rate the severity of this patient's skin and/or joint tightening on the following scale, where 0 is not at all severe and 10 is the most severe symptoms possible:
 
 
 0	1	2	3	4	5	6	7	8	9	10	
 
 Symptoms not at all severe	Most severe symptoms possible	
 
					0	1	2	3	4	5	6	7	8	9	10	Symptoms not at all severe					Most severe symptoms possible					
0	1	2	3	4	5	6	7	8	9	10																
Symptoms not at all severe					Most severe symptoms possible																					
EYES	 No symptoms	 Mild dry eye symptoms not affecting ADL (requirement of lubricant eye drops \leq 3 x per day)	 Moderate dry eye symptoms partially affecting ADL (requiring lubricant eye drops > 3 x per day or punctal plugs), WITHOUT new vision impairment due to KCS	 Severe dry eye symptoms significantly affecting ADL (special eyewear to relieve pain) OR unable to work because of ocular symptoms OR loss of vision due to KCS																						
 Abnormality present but explained entirely by non-GVHD documented cause (specify): _____																										
LUNGS	 No symptoms	 Mild symptoms (shortness of breath after climbing one flight of steps)	 Moderate symptoms (shortness of breath after walking on flat ground)	 Severe symptoms (shortness of breath at rest; requiring O_2)																						
 Abnormality present but explained entirely by non-GVHD documented cause (specify): _____																										

Chronic GvHD Activity Assessment (Clinician) Form A

	SCORE 0	SCORE 1	SCORE 2	SCORE 3
JOINTS AND FASCIA	 No symptoms	 Mild tightness of arms or legs, normal or mild decreased range of motion (ROM) AND not affecting ADL	 Tightness of arms or legs OR joint contractures, erythema thought due to fasciitis, moderate decrease ROM AND mild to moderate limitation of ADL	 Contractures WITH significant decrease of ROM AND significant limitation of ADL (unable to tie shoes, button shirts, dress self etc.)
 Abnormality present but explained entirely by non-GVHD documented cause (specify): _____				

Shoulder	1 (Worst)	2	3	4	5	6	7 (Normal)	 Not done
Elbow	1 (Worst)	2	3	4	5	6	7 (Normal)	 Not done
Wrist/finger	1 (Worst)	2	3	4	5	6	7 (Normal)	 Not done
Ankle	1 (Worst)	2	3	4 (Normal)				 Not done

Abnormality present but explained entirely by non-GVHD documented cause (specify): _____

16.7 APPENDIX G: PARTICIPANT SELF-ASSESSMENT QUESTIONNAIRES

FORM B	Today's Date: _____	MR#/Name: _____																					
CHRONIC GVHD ACTIVITY ASSESSMENT-PATIENT SELF REPORT																							
Symptoms Please rate how severe the following symptoms have been in the last seven days . Please fill in the circle below from 0 (symptom has not been present) to 10 (the symptom was as bad as you can imagine it could be) for each item.	Not Present 0 1 2 3 4 5 6 7 8 9 10	As Bad As You Can Imagine																					
Your skin itching at its WORST?																							
Your skin and/or joint tightening at their WORST?																							
Your mouth sensitivity at its WORST?																							
Your genital discomfort at its WORST? (Women – vagina, vulva, or labia) (Men – penis)																							
Eyes	What is your main complaint with regard to your eyes?																						
	Please rate how severe this symptom is, from 0 (not at all severe) to 10 (most severe):																						
	0 1 2 3 4 5 6 7 8 9 10																						
Patient Global Ratings: 
1. Overall, do you think that your chronic graft versus host disease is mild, moderate or severe? 1=mild 2=moderate 3=severe
 
2. Please circle the number indicating how severe your chronic graft versus host disease symptoms are, where 0 is cGvHD symptoms that are not at all severe and 10 is the most severe chronic GvHD symptoms possible.
 
 
 0	1	2	3	4	5	6	7	8	9	10	
 
 
cGvHD symptoms not at all severe
 
Most severe cGvHD symptoms possible
 
3. Compared to a month ago, overall would you say that your cGvHD symptoms are:
 
+3= Very much better +2= Moderately better +1=A little better 0= About the same -1=A little worse -2=Moderately worse -3=Very much worse
													0	1	2	3	4	5	6	7	8	9	10
0	1	2	3	4	5	6	7	8	9	10													

Lee Chronic GVHD Symptom Scale

	Not at all	Slightly	Moderately	Quite a bit	Extremely
SKIN:					
a. Abnormal skin color	0	1	2	3	4
b. Rashes	0	1	2	3	4
c. Thickened skin	0	1	2	3	4
d. Sores on skin	0	1	2	3	4
e. Itchy skin	0	1	2	3	4
EYES AND MOUTH:					
f. Dry eyes	0	1	2	3	4
g. Need to use eye drops frequently	0	1	2	3	4
h. Difficulty seeing clearly	0	1	2	3	4
i. Need to avoid certain foods due to mouth pain	0	1	2	3	4
j. Ulcers in mouth	0	1	2	3	4
k. Receiving nutrition from an intravenous line or feeding tube	0	1	2	3	4
BREATHING:					
l. Frequent cough	0	1	2	3	4
m. Colored sputum	0	1	2	3	4
n. Shortness of breath with exercise	0	1	2	3	4

	Not at all	Slightly	Moderately	Quite a bit	Extremely
o. Shortness of breath at rest	0	1	2	3	4
p. Need to use oxygen	0	1	2	3	4
EATING AND DIGESTION:					
q. Difficulty swallowing solid foods	0	1	2	3	4
r. Difficulty swallowing liquids	0	1	2	3	4
s. Vomiting	0	1	2	3	4
t. Weight loss	0	1	2	3	4
MUSCLES AND JOINTS:					
u. Joint and muscle aches	0	1	2	3	4
v. Limited joint movement	0	1	2	3	4
w. Muscle cramps	0	1	2	3	4
x. Weak muscles	0	1	2	3	4
ENERGY:					
y. Loss of energy	0	1	2	3	4
z. Need to sleep more/take naps	0	1	2	3	4
aa. Fevers	0	1	2	3	4
MENTAL AND EMOTIONAL:					
bb. Depression	0	1	2	3	4
cc. Anxiety	0	1	2	3	4

Abbreviated Title: Ibrutinib for Chronic GvHD

Version Date: 4/26/2023

	Not at all	Slightly	Moderately	Quite a bit	Extremely
dd. Difficulty sleeping	0	1	2	3	4

Short Form Health Survey (SF-36)

Your Health and Well-Being

This survey asks for your views about your health. This information will help keep track of how you feel and how well you are able to do your usual activities.
Thank you for completing this survey!

For each of the following questions, please mark an in the one box that best describes your answer.

1. In general, would you say your health is:

Excellent	Very good	Good	Fair	Poor
 1	 2	 3	 4	 5

2. Compared to one year ago, how would you rate your health in general now?

Much better now than one year ago	Somewhat better now than one year ago	About the same as one year ago	Somewhat worse now than one year ago	Much worse now than one year ago
 1	 2	 3	 4	 5

3. The following questions are about activities you might do during a typical day. Does your health now limit you in these activities? If so, how much?

	Yes, limited a lot	Yes, limited a little	No, not limited at all
	▼	▼	▼

- a Vigorous activities, such as running, lifting heavy objects, participating in strenuous sports 1 2 3
- b Moderate activities, such as moving a table, pushing a vacuum cleaner, bowling, or playing golf 1 2 3
- c Lifting or carrying groceries 1 2 3
- d Climbing several flights of stairs 1 2 3
- e Climbing one flight of stairs 1 2 3
- f Bending, kneeling, or stooping 1 2 3
- g Walking more than a mile 1 2 3
- h Walking several hundred yards 1 2 3
- i Walking one hundred yards 1 2 3
- j Bathing or dressing yourself 1 2 3

4. During the past 4 weeks, how much of the time have you had any of the following problems with your work or other regular daily activities as a result of your physical health?

	All of the time	Most of the time	Some of the time	A little of the time	None of the time
	▼	▼	▼	▼	▼

- a. Cut down on the amount of time you spent on work or other activities 1..... 2..... 3..... 4..... 5
- b. Accomplished less than you would like 1..... 2..... 3..... 4..... 5
- c. Were limited in the kind of work or other activities 1..... 2..... 3..... 4..... 5
- d. Had difficulty performing the work or other activities (for example, it took extra effort) 1..... 2..... 3..... 4..... 5

5. During the past 4 weeks, how much of the time have you had any of the following problems with your work or other regular daily activities as a result of any emotional problems (such as feeling depressed or anxious)?

	All of the time	Most of the time	Some of the time	A little of the time	None of the time
	▼	▼	▼	▼	▼

- a. Cut down on the amount of time you spent on work or other activities 1..... 2..... 3..... 4..... 5
- b. Accomplished less than you would like 1..... 2..... 3..... 4..... 5
- c. Did work or other activities less carefully than usual 1..... 2..... 3..... 4..... 5

6. During the past 4 weeks, to what extent has your physical health or emotional problems interfered with your normal social activities with family, friends, neighbors, or groups?

Not at all	Slightly	Moderately	Quite a bit	Extremely
				
 1	 2	 3	 4	 5

7. How much bodily pain have you had during the past 4 weeks?

None	Very mild	Mild	Moderate	Severe	Very severe
					
 1	 2	 3	 4	 5	 6

8. During the past 4 weeks, how much did pain interfere with your normal work (including both work outside the home and housework)?

Not at all	A little bit	Moderately	Quite a bit	Extremely
				
 1	 2	 3	 4	 5

9. These questions are about how you feel and how things have been with you during the past 4 weeks. For each question, please give the one answer that comes closest to the way you have been feeling. How much of the time during the past 4 weeks...

All of the time	Most of the time	Some of the time	A little of the time	None of the time
				

a Did you feel full of life? 1 2 3 4 5

b Have you been very nervous? 1 2 3 4 5

c Have you felt so down in the dumps that nothing could cheer you up? 1 2 3 4 5

d Have you felt calm and peaceful? 1 2 3 4 5

e Did you have a lot of energy? 1 2 3 4 5

f Have you felt downhearted and depressed? 1 2 3 4 5

g Did you feel worn out? 1 2 3 4 5

h Have you been happy? 1 2 3 4 5

i Did you feel tired? 1 2 3 4 5

10. During the past 4 weeks, how much of the time has your physical health or emotional problems interfered with your social activities (like visiting with friends, relatives, etc.)?

All of the time	Most of the time	Some of the time	A little of the time	None of the time
				
 1	 2	 3	 4	 5

11. How TRUE or FALSE is each of the following statements for you?

Definitely true	Mostly true	Don't know	Mostly false	Definitely false
▼	▼	▼	▼	▼

- a I seem to get sick a little easier than other people 1 2 3 4 5
- b I am as healthy as anybody I know 1 2 3 4 5
- c I expect my health to get worse 1 2 3 4 5
- d My health is excellent 1 2 3 4 5

Thank you for completing these questions!

16.8 APPENDIX H: RESPONSE DETERMINATION FOR CHRONIC GVHD TRIALS BASED ON CLINICIAN ASSESSMENTS

Organ	Complete Response	Partial Response	Progression
Skin	NIH Skin Score 0 after previous involvement	Decrease NIH Skin Score by 1 or more points	Increase in NIH Skin Score by 1 or more points, except 0 to 1
Eyes	NIH Eye Score 0 after previous involvement	Decrease in NIH Eye Score by 1 or more points	Increase in NIH Eye Score by 1 or more points, except 0 to 1
Mouth	NIH Modified OMRS 0 after previous involvement	Decrease in NIH Modified OMRS of 2 or more points	Increase in NIH Modified OMRS of 2 or more points
Esophagus	NIH Esophagus Score 0 after previous involvement	Decrease in NIH Esophagus Score by 1 or more points	Increase in NIH Esophagus Score by 1 or more points, except 0 to 1
Upper GI	NIH Upper GI Score 0 after previous involvement	Decrease in NIH Upper GI Score or more points	Increase in NIH Upper GI Score by 1 or more points, except 0 to 1
Lower GI	NIH Lower GI Score 0 after previous involvement	Decrease in NIH Lower GI Score by 1 or more points	Increase in NIH Lower GI Score by 1 or more points, except from 0 to 1
Liver	Normal ALT, alkaline phosphatase, and Total bilirubin after previous elevation of 1 or more	Decrease by 50%	Increase by 2 x ULN
Lungs	
 – Normal %FEV1, alkaline phosphatase, and Total bilirubin after previous elevation of 1 or more – If PFTs not available, NIH Lung Symptom Score 0 after previous involvement 	
 – Increase by 10% predicted absolute value of %FEV1 – If PFTs not available, decrease in NIH Lung Symptom Score by 1 or more points 	
 – Decrease by 10% predicted absolute value of %FEV1 – If PFTs not available, increase in NIH Lung Symptom Score by 1 or more points, except 0 to 1
Joints and fascia	Both NIH Joint and Fascia Score 0 and P-ROM score 25 after previous involvement by at least 1 measure	Decrease in NIH Joint and Fascia Score by 1 or more points or increase in P-ROM score by 1 point for any site	Increase in NIH Joint and Fascia Score by 1 or more points or decrease in P-ROM score by 1 point for any site
Global	Clinician overall severity score 0	Clinician overall severity score decreases by 2 or more points on a 0-10 scale	Clinician overall severity score increases by 2 or more points on a 0-10 scale

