6.3.1 Response Criteria

Efficacy will be assessed using NIH consensus criteria measuring for therapeutic response in clinical trials for chronic GvHD. The calculations for CR, PR and progressive disease are provided in [Appendix H](#).

- **CR** is defined as complete resolution in all of signs and symptoms at all affected organs or tissues.
- **PR** is defined as improvement in ≥ 1 organ or tissue with no progression in any other affected organ or tissue.
- **Stable Disease (SD)** is defined as no change in chronic GvHD.
- **Flare** is defined as exacerbation of chronic GvHD manifestations during withdrawal of immunosuppressive therapy which do not exceed those at the beginning of the trial and improves after reinstatement of previous treatment. For the purpose of this study, any flare which requires change or intensification of systemic therapy beyond the one per protocol allowed steroid pulse within initial four weeks will be considered a therapy failure.
- **Progressive disease (PD)** is defined as failure of therapy to control chronic GvHD. Participants who progress prior to 6 months evaluation will be also evaluable for the primary efficacy endpoint.
- **Mixed response** is defined as an improvement in some organs but worsening in others and will be categorized as progressive disease.

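### The PFT-based lung complete-response rule in Appendix H carries liver-test conditions, which mis-scores lung CR and, in one narrow case, the CR+PR count

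*Combined protocol and SAP*

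**What the plan says.** Section 6.3.1 of the protocol makes Appendix H the operative scoring rule: "The calculations for CR, PR and progressive disease are provided in" that appendix. No other section restates or corrects the lung rule.

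The Appendix H entries that matter are:

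- Liver, complete response: "Normal ALT, alkaline phosphatase, and Total bilirubin after previous elevation of 1 or more".
- Lungs, complete response with PFTs: "Normal %FEV1, alkaline phosphatase, and Total bilirubin after previous elevation of 1 or more".
- Lungs, complete response without PFTs: "If PFTs not available, NIH Lung Symptom Score 0 after previous involvement".
- Lungs, partial response with PFTs: "Increase by 10% predicted absolute value of %FEV1".
- Lungs, progression with PFTs: "Decrease by 10% predicted absolute value of %FEV1".

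Appendix E grades lung severity on FEV1 alone: "In lung: FEV1 is used instead of clinical score for calculating global severity". Note 6 to the Appendix K study calendar schedules PFTs at the six-month evaluation (C7D1), so the PFT branch governs at the primary time point. PFTs at 12 and 24 months are optional.

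The upper GI partial-response cell has a separate slip: "Decrease in NIH Upper GI Score or more points". The neighbouring rows say by how many points.

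**The concern.** The lung CR cell has the form of the liver CR cell, with one analyte exchanged. It asks for normal alkaline phosphatase and total bilirubin, which do not measure lung disease. It also asks for an earlier elevation, and a diseased FEV1 is low, so only the two liver tests can supply one.

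Overall CR in section 6.3.1 needs resolution in every affected organ. A lung that cannot be scored CR therefore removes overall CR, and with it the start date for duration of CR in section 6.3.2. If the lung also misses the PR rule, a responder may be lost from the primary endpoint. The decisions turn on 3 versus 4 of 14 and 7 versus 8 of 25, and non-response at six months is a criterion for removal from protocol therapy (section 3.8.1).

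The trial is multi-center and scored by physicians or nurse practitioners. Some may follow the cell and others may silently correct it. Either way, the scoring of the primary endpoint varies without a record.

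**Working it through.** **1. Design figures (section 10.2).** Inputs: p0 = 0.20, p1 = 0.45; stop at 3 or fewer responders of 14; success at 8 or more of 25.

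- Early termination at p0 = Σ(x=0..3) C(14,x)·0.2^x·0.8^(14−x) = 0.0440 + 0.1539 + 0.2501 + 0.2501 = 0.698. This reproduces the stated 69.8%.
- Success probability = Σ(x=4..14) P[Bin(14,p) = x]·P[Bin(11,p) ≥ 8−x]. This gives 0.093 at p0 and 0.903 at p1, within the stated error limits of 0.10.

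The lung cell does not enter these figures. They are the base for step 5.

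**2. The rules side by side.** Of the five lung rules with content in Appendix H that bear on response (CR by PFT, CR by symptoms, PR by PFT, PR by symptoms, progression), only CR by PFT mentions a liver test. The liver conditions are added to the FEV1 condition, so the cell as written can remove a lung CR but never create one.

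**3. Scoring cases.** Appendix H does not define normal %FEV1. I assume Appendix D lung score 0, FEV1 of 80% or more. PR needs a gain of at least 10 points. *Unmet* means that neither alkaline phosphatase nor bilirubin was ever raised, or that one of them is raised now.

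| FEV1, baseline to follow-up | Gain | As written, liver condition unmet | As written, earlier elevation resolved | On FEV1 alone |
|---|---|---|---|---|
| 55% to 85% | 30 | PR | CR | CR |
| 68% to 82% | 14 | PR | CR | CR |
| 74% to 81% | 7 | unchanged | CR | CR |
| 72% to 80% | 8 | unchanged | CR | CR |
| 60% to 68% | 8 | unchanged | unchanged | unchanged |

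In the first two rows only the CR/PR label moves. In the third and fourth the lung drops out of CR+PR.

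**4. Who is lost from CR+PR.** Reaching 80% with a gain under 10 points requires 80 − baseline < 10, so a baseline above 70%: 71% to 79% in whole points. Section 6.3.1 grants PR for improvement in one organ with no progression elsewhere, and an unchanged lung is not progression. Any other improving organ therefore keeps the participant a responder. Loss needs all three together: normalisation by under 10 points, no qualifying improvement elsewhere, and the liver-test condition unmet. Appendix E classes lung score 1 (FEV1 60–79% in Appendix D) as moderate disease without any other organ, so a lung-only participant in this band is eligible.

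**5. Range of consequence.** The documents give no frequency. With an assumed share f of true responders lost, the effective rate is 0.45·(1−f):

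| f | Rate | Probability of success |
|---|---|---|
| 0% | 0.450 | 0.903 |
| 2% | 0.441 | 0.888 |
| 5% | 0.4275 | 0.862 |
| 10% | 0.405 | 0.811 |

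Since responses can only be lost, the type I error can only fall. One participant is 1/25 = 4 percentage points, as for any single misclassification.

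**The case against.** **The cell may be a reading fault.** The text examined was read from PDF by a program. In that text, reference 33 carries the ending of the neighbouring reference 32 before its own, so a fluent sentence and an intact liver row do not exclude copying between rows. This stands as a reason to check the source PDF. It does not show that the cell is an artefact: the line is complete and has %FEV1 where the liver row has ALT.

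**Trained assessors will apply the NIH 2014 criteria and ignore the liver tests.** Probably many would. But the protocol names this table as the calculation, and unrecorded correction by individual assessors does not make the stated rule sound.

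**The endpoint is CR+PR, with no separate CR-rate analysis planned.** This stands and limits the weight of the point. Duration of response is an exploratory objective, and section 6.3.2 defines duration of CR.

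**Stronger readings a reader might infer.** One is that lung responses in general are mis-scored. They are not: PR, progression and the fallback use lung measures only. Another is that liver involvement rules out lung CR. It does not: an alkaline phosphatase or bilirubin elevation that has resolved satisfies the literal rule. Where liver GvHD persists, overall CR already fails on the liver row. A third is that every participant with baseline FEV1 of 71–79% who normalises by under 10 points is lost as a responder. Section 6.3.1 does not support that, because improvement in another organ is enough for PR.

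**Conclusion.** The concern holds for PFT-based lung complete response. As written, the cell denies lung CR to a participant with no earlier alkaline phosphatase or bilirubin elevation, or with either still raised from any cause. Its main effect is on the CR/PR split and duration of CR.

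The effect on the primary CR+PR count is confined to the three-condition case in step 4 of the working. That case is possible under the eligibility criteria, but its frequency cannot be derived from the documents. The sensitivity figures show direction and scale for assumed losses and are not an estimate of bias. The error works against the drug, and the two-stage design figures are unaffected.

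The conclusion rests on two assumptions: that the cell reads the same in the source PDF, and that normal %FEV1 means 80% or more. The point is small in expected effect, but it concerns an operative endpoint rule and is worth correcting.

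**What to change.** 1. Confirm the lung CR cell against the source PDF.
2. If it stands, replace the PFT line with *Normal %FEV1 after previous involvement*, which matches the form of the fallback line in the same cell.
3. Define normal %FEV1 in Appendix H, for example by reference to Appendix D lung score 0. Without this, cases such as 72% to 80% stay open even after the liver tests are removed.
4. Re-score any participant already assessed by PFT whose FEV1 became normal, including those recorded as lung PR or unchanged, and record the changes.
5. In the same amendment, restore the missing *by 1* in the upper GI partial-response cell. This is clerical.

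The cost is two table cells, one definition and a short re-check of existing lung assessments. Sample size, decision rules and visit schedule do not change.
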